Schedule of training sessions. All enrolled participants will be asked to complete 48 training sessions over 10 weeks. The sessions will last approximately 20-30 minutes and will be completed at home or wherever the participant can obtain computer access. If the participant has no means of accessing a computer, sessions can be completed in-person in the research laboratory. Participants will be encouraged to complete 6 sessions a week, 1 per day, to reach a total of 48 by the end of the 10-week period. While each group will complete the same number of sessions to control for possible dosage effects, the content of the sessions will vary by study group. Each condition will include 8 unique Lumosity games.

Active Cognitive Training (ACT). Sessions will include games from Lumosity that are designated as targeting working memory. One training session will be comprised of a randomly generated subset of 4 of the 8 working memory games, each played twice back-to-back.

Control Training (CON). The sessions will be in the same format as the ACT group, but will utilize other Lumosity games that do not target working memory. These games will be the same length as the working memory games and participants will complete the same number of randomly generated games per session (4 of the 8 games, played twice back-to-back).

Post-training Assessment. After completing the 48th training session, or at the end of the 10-week training window, participants will complete a post-training assessment. This 3-hour visit will occur within 1 week of the final training session and will consist of a battery identical to the baseline assessment. Alternate forms of neuropsychological tests involving memory will be used to avoid effects related to repeated testing. Participants will also complete a process measure to describe their experiences of the intervention and provide feedback on perceived benefits, barriers to completing sessions, and the length, number, and content of sessions. This assessment includes open-ended questions and ratings of satisfaction and helpfulness.

One-month Follow-up Assessment. One month after the post-training assessment, participants will complete a follow-up assessment. This 3-hour visit will consist of a battery identical to the baseline assessment. Alternate forms of neuropsychological tests involving memory will be used to avoid any effects related to repeated testing.

Human Subjects Protections

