Initial analyses will confirm the psychometric properties of the assessments, and scale scores will be constructed. Data distributions will be checked to determine if they meet the assumptions of the analytic models, and transformations will be performed when necessary to improve distributional qualities. Preliminary analyses will compare study groups on demographic and other characteristics obtained in the screening and baseline assessments to identify possible failures in random assignment, which would be statistically controlled for in subsequent analyses. We will also test for any differential attrition across groups at both follow-ups. All analyses will be repeated with other substance use added as a covariate.

Hypothesis testing (Aim 1). Using an intent-to-treat analysis, we will investigate the differential impact of condition (ACT vs. CON) at the post-training assessment by performing a 2 (Condition) by 2 (Time) general linear model (GLM) analysis on the main outcome measures of working memory (mean T-score on the 3-test battery) and delay discounting (natural log k-value). Time will be a within subjects factor defined by baseline versus post-training assessment. The analysis will be repeated, adding the 1-month follow-up in a 2 (Condition) by 3 (Time) GLM to detect differential effects of the two conditions on outcomes through the follow-up period. Significant interactions of Condition and Time are predicted. To examine the specificity of the cognitive training intervention, we will use the same models to test for group differences on performance in other cognitive domains (e.g., verbal fluency, processing speed) and other measures of decision making (i.e., contingency learning, risk taking propensity).

Additional analyses will be restricted to participants who were randomized to ACT. First, we will examine predictors of treatment response (moderators) based on sample characteristics. We will use linear regression to predict change in the main outcome variables (working memory and delay discounting), with potential moderators entered separately as predictors. Second, we will use linear regression to evaluate the effect of treatment dosage (number of sessions completed) on change in the outcome variables. Finally, if intervention effects are identified on main outcomes, we will test whether effects were mediated by performance on the working memory training modules using bootstrap analyses.³⁶⁻³⁸

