Acceptability (Aim 2). We will examine participant ratings of satisfaction with the cognitive training intervention, as well as their perception of its benefits and barriers to completing sessions. The intervention will be considered acceptable if participant ratings are high (>3.5 on a 5-point scale). We will also calculate the average number of sessions completed and determine the proportion of participants who successfully completed the intervention (defined as completing ≥36 of the 48 total sessions). The intervention will be considered acceptable to the target population if ≥80% complete the intervention.

Exploratory analyses (Aim 3): To investigate the impact of the intervention on risk behaviors, we will use the same GLM models described above to test for differences by condition on cocaine use (number of days of use), sexual risk (HRBS sex risk score), and adherence to ARVs (percent medication adherence).

Clinical Trials Registration

This study is registered at <http://www.ClinicalTrials.gov> (Identifier: NCT: NCT02909101).

References

4. RAND Corporation. *HIV Cost and Services Utilization Study (HCSUS) baseline questionnaire*. Santa Monica, CA: RAND Corporation; 2007.
5. Wilkinson GS, Robertson GJ. *Wide Range Achievement Test-4 (WRAT-4)*. Lutz, FL: Psychological Assessment Resources.
6. Derogatis LR. *Brief Symptom Inventory: Administration, Scoring, and Procedures Manual*. 3rd ed. Minneapolis, MN: National Computer Systems, Inc.; 1993.

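### The follow-up analysis rests on a 2-df Condition by Time interaction with no contrast at 1 month, so a significant result does not show whether the training effect was kept, lost or delayed

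*Combined protocol and SAP*

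**What the plan says.** Participants are assessed at baseline, after training and once more: "One month after the post-training assessment, participants will complete a follow-up assessment" (One-month Follow-up Assessment).

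Under Statistical analyses, Hypothesis testing (Aim 1), there are two models for working memory (primary) and delay discounting (secondary). In the first, "Time will be a within subjects factor defined by baseline versus post-training assessment". That factor has two levels, so its interaction with condition is a single contrast: the arm difference in change to post-training. The second repeats the analysis with the 1-month visit added, "in a 2 (Condition) by 3 (Time) GLM to detect differential effects of the two conditions on outcomes through the follow-up period". The expected result for both is given in one sentence: "Significant interactions of Condition and Time are predicted".

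The section names no arm comparison of change from baseline to 1 month or from post-training to 1 month. It gives no rule for following up a significant interaction, no covariance structure and no sphericity correction. The same models serve the other cognitive domains and decision-making measures. For Aim 3, "we will use the same GLM models described above to test for differences by condition" on cocaine use, sexual risk and antiretroviral adherence.

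**The concern.** The null hypothesis of the three-visit interaction is that the ACT-CON difference is the same at every visit. Any departure counts against it. A difference that appears after training and persists is one such departure. So is a difference that appears after training and is gone a month later, and so is one that first appears at 1 month.

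The first model already tests the post-training effect directly. In the second model a post-training effect can by itself produce significance, whatever happens at 1 month. The third visit then has no test that speaks specifically to it.

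At stake is the Aim 1 statement about follow-up for working memory and delay discounting. An effect that faded within a month could give the predicted significant interaction. With no contrast chosen in advance, the reading of that result would be settled after the data are seen.

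**Working it through.** **Inputs.** From the documents: two arms, three visits, the 2 by 3 model and the predicted interaction. Not in the documents, so assumed: n = 20, 30 or 50 per arm with 1:1 allocation; post-training effect d = 0.5 SD; correlation between visits rho = 0.6 or 0.8 (unequal sets further below); alpha 0.05, two-sided for the contrast; complete data. The plan states no power figure, so there is none to reproduce.

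**Step 1: equal variances and correlations.** Let delta_t be the ACT-CON difference at visit t, in SD units. The interaction F test has

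lambda = (n/2) × Σ(delta_t − mean delta)² / (1 − rho), with df 2 and 2(2n − 2).

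| Pattern (baseline, post, 1 month) | Mean | Sum of squared deviations |
|---|---|---|
| Kept (0, d, d) | 2d/3 | (4/9 + 1/9 + 1/9)d² = (2/3)d² |
| Lost (0, d, 0) | d/3 | (1/9 + 4/9 + 1/9)d² = (2/3)d² |
| Delayed (0, 0, d) | d/3 | (1/9 + 1/9 + 4/9)d² = (2/3)d² |
| Half kept (0, d, d/2) | d/2 | (1/4 + 1/4 + 0)d² = (1/2)d² |

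The first three patterns have the same lambda, and so the same power, for any n, d and rho.

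For n = 30, d = 0.5, rho = 0.6: lambda = 15 × (2/3)(0.25)/0.4 = 6.25 and power is 59.1% for kept, lost or delayed. For half kept, lambda = 15 × 0.125/0.4 = 4.69 and power is 46.6%. A partly retained effect is thus less likely to reach significance than one that has wholly gone.

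**Step 2: the 1-df contrast.** For the arm difference in change from baseline to 1 month, the noncentrality is d/√(2(1 − rho) × 2/n) on 2n − 2 df. For the same case it is 0.5/√(0.8 × 2/30) = 2.17 on 58 df, which gives power of 56.7% if the effect is kept. If it is lost the noncentrality is 0, and the rejection rate is 5%.

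| rho | n per arm | Interaction, kept or lost | Contrast, kept | Contrast, lost |
|---|---|---|---|---|
| 0.6 | 20 | 41.6% | 40.6% | 5% |
| 0.6 | 30 | 59.1% | 56.7% | 5% |
| 0.6 | 50 | 82.6% | 79.0% | 5% |
| 0.8 | 20 | 71.8% | 68.3% | 5% |
| 0.8 | 30 | 88.8% | 85.3% | 5% |
| 0.8 | 50 | 98.7% | 97.5% | 5% |

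**Step 3: unequal correlations.** The multivariate test has lambda = (n/2) v′V⁻¹v, with df 2 and 2n − 3. Here v holds the arm differences in change from baseline at the two later visits, and V is the covariance matrix of those changes. With n = 30 and d = 0.5:

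- Baseline-post 0.7, post-1 month 0.8, baseline-1 month 0.6. V has diagonal 0.6 and 0.8, off-diagonal 0.5 and determinant 0.23. Kept: 15 × 0.25 × (0.6 + 0.8 − 1.0)/0.23 = 6.52, power 60%. Lost: 15 × 0.25 × 0.8/0.23 = 13.04, power 89%.
- Baseline-post 0.7, post-1 month 0.7, baseline-1 month 0.8. V has diagonal 0.6 and 0.4, off-diagonal 0.2 and determinant 0.20. Kept: 15 × 0.25 × (0.6 + 0.4 − 0.4)/0.20 = 11.25, power 84%. Lost: 15 × 0.25 × 0.4/0.20 = 7.5, power 66%.
- Baseline-post 0.8, the other two 0.7: 84% for both.

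The order of kept and lost thus depends on whether the 1-month score correlates more with post-training or with baseline. In each of these cases a lost effect is still declared significant well over half the time.

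**The case against.** The best defence is that the plan claims less than a reader might take from it. A reader might infer that a significant three-visit interaction will be treated as proof of a lasting effect. The documents do not say so. The sentence on significant interactions is a prediction, neither hypothesis under Specific Aims mentions persistence, and Study design gives the general purpose of all three assessments as evaluating the program's impact. The model also contains the needed contrast, and many analysts would look at the visit means after a significant interaction. Nothing in the plan forbids that.

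This shows that the model is sound and that a misreport is possible, not certain. It does not supply the missing test. The plan names neither the comparison nor the rule, and fixing both before the data are seen is the job of the analysis section.

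A reader might also infer that a lost effect is always as likely as a kept one to give significance. That is exact under equal variances and correlations, or for the multivariate test with equal variances when the 1-month score correlates equally with the other two visits. It is not general: the second case in step 3 favours a kept effect. That pattern is less plausible, since the last two visits are one month apart after a training window of up to 10 weeks, but the documents give no correlations to settle it.

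Finally, this is described as a test of feasibility and preliminary efficacy, and the Aim 3 outcomes are exploratory. That limits the consequence there. It does not remove it for the two Aim 1 outcomes, which appear under the hypothesis-testing heading.

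**Conclusion.** The point holds as a defect in how the follow-up result can be read. The only stated test involving the 1-month visit cannot tell a kept effect from a lost or delayed one, and no contrast that could do so is pre-specified.

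The equality of power for kept and lost effects under equal variances and correlations is algebra and needs no assumed sample size. Every percentage above rests on assumed n, effect size, correlations, alpha and complete data. Under unequal correlations the size and direction of the gap change, but the non-specificity remains.

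The primary question, working memory at post-training, is not touched: the two-visit interaction is a 1-df test of that change. The point should be corrected before analysis, but it ranks below anything that affects the primary result.

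**What to change.** In Statistical analyses, Hypothesis testing (Aim 1), keep the three-visit model and add:

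- The ACT-CON difference in change from baseline to 1 month, estimated from that model as a 1-df contrast with a 95% confidence interval, is the basis for any claim of an effect at follow-up on working memory or delay discounting.
- The ACT-CON difference in change from post-training to 1 month is reported descriptively, as the measure of how much of the effect was lost.

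The same baseline-to-1-month contrast can be reported for the specificity and Aim 3 outcomes, labelled exploratory.

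The cost is one or two sentences, with no new data, visits or participants. For a fully kept effect, power falls by about 1 to 4 points in the equal-correlation cases tabulated above (for example 59.1 − 56.7 = 2.4 points). The loss can be larger when correlations are unequal: with baseline-post 0.8 and the other two 0.7, at n = 30 and d = 0.5, the contrast has 69% against 84% for the multivariate interaction test. That extra power, however, belongs to a test that gives the same 84% when the effect has gone.

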COGNITIVE TRAINING TO REDUCE IMPULSIVITY IN HIV-INFECTED COCAINE USERS

NCT02909101

Study Protocol with Statistical Analysis Plan

VERSION DATE: April 13, 2018

Specific Aims

This study tests the feasibility and preliminary efficacy of a computerized cognitive training program to improve working memory and decrease impulsivity (delay discounting) among HIV-infected individuals. The specific aims are to

- (1) Investigate the effects of the cognitive training intervention on working memory (primary outcome) and delay discounting (secondary outcome) in HIV-infected persons;
- (2) Establish the acceptability of computerized cognitive training among HIV-infected past or present cocaine users; and
- (3) Examine the effect of cognitive training on HIV risk behaviors, including cocaine use, risky sex, and medication adherence (exploratory outcomes).

We hypothesize that: (1) Participants assigned to active cognitive training (ACT), compared to those in the attention-matched control group (CON), will have greater improvements in working memory and reductions in delay discounting; (2) Participants assigned to ACT, compared to those in CON, will have greater reductions in HIV risk behaviors, including improvements in medication adherence.

Study design

The proposed study will test the efficacy of a cognitive training program to improve working memory in a sample of HIV-infected cocaine users. We will evaluate the effects of this cognitive training intervention on working memory, delay discounting, and HIV risk behaviors. We will first screen participants for eligibility. Eligible participants will be assigned to one of two groups (ACT or CON) and will complete 48 training sessions over 10 weeks. Participants assigned to ACT will complete computerized games designed to enhance working memory, while those assigned to the attention-matched CON will complete games that use other brain attributes. We will be using a web-based program, Lumosity (Lumos Labs, Inc.; <http://www.lumosity.com>). Lumosity is available to the public and offers user-friendly cognitive training games targeting different brain areas. We have developed a contract with Lumosity tailoring the website to fit our study's needs. All participants will complete assessments at baseline, post-training, and 1-month follow-up to evaluate the impact of the training program. Staff members conducting assessments will be blinded to treatment condition in order to ensure no biases occur during testing.

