research assistants will administer clinical interviews and neuropsychological tests of working memory. Additional questionnaires will be administered using audio computer-assisted self-interview (ACASI) technology. The urine toxicology screen will be used to verify self-reports of recent use of cannabis, cocaine, stimulants, opioids, and benzodiazepines.

In-person Interview and Testing. In-person interview and testing (lasting approximately 90 minutes) will be conducted by trained research personnel. Interviews will assess substance use and impairment, psychiatric history, HIV testing, staging and treatment history, medication adherence, substance use, sexual behaviors, and psychiatric history.

ACASI. Questionnaires will be programmed using QDS™ software. The computer will display one question at a time, and participants will respond using a mouse. For patients who prefer not to read, the computer will read the questions and responses using prerecorded sound files. The ACASI will last approximately 30 minutes will include items related to demographics, anxiety and depression, HIV symptoms, stimulant craving, and medical history.

Baseline Assessment. Eligible participants will be invited back on a separate day for a 3-hour baseline assessment. At the beginning of this visit, participants will complete a breathalyzer, urine drug testing and pregnancy testing if indicated. Participants will then complete an assessment battery of standardized measures that includes face-to-face interviews, questionnaires, decision making tasks, and neuropsychological testing (**Table 2**).

Neurocognition. A 60-minute comprehensive neuropsychological battery will assess functioning across performance domains and estimates premorbid intellectual functioning. All tests have excellent clinical validity with large national norming samples and will be scored using standard procedures.

Table 1. Eligibility Screening Measures	
Construct	Instrument(s)
In-person Interview and Testing	
Substance Use & Impairment	Addiction Severity Index-LITE ^{1,2}
Substance Use Disorders	Structured Clinical Interview for DSM-5 (SCID-5) Module E ³
Psychiatric history	SCID-5 Modules A and B ³
HIV Testing and Staging	HIV Cost and Services Utilization Study ⁴
Literacy	Wide Range Achievement Test-4 Word Reading Subtest ⁵
ACASI	
Patient Characteristics	Demographics
Anxiety/Depression	Brief Symptom Inventory ⁶
HIV Symptoms	HIV Symptoms Index ⁷
PTSD Symptoms	Post-Traumatic Stress Disorder Checklist-5 ⁸

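### The specificity analysis never tests whether the training effect on working memory is larger than the effect in other domains, so a general benefit could be read as specific.

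*Combined protocol and SAP*

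**What the plan says.** Under Statistical analyses, Hypothesis testing (Aim 1), the main analysis is described as "performing a 2 (Condition) by 2 (Time) general linear model (GLM) analysis on the main outcome measures of working memory" and delay discounting, then repeated with the 1-month visit as a third time point. The same paragraph then gives specificity as a purpose and says "we will use the same models to test for group differences on performance in other cognitive domains", with verbal fluency and processing speed given only as examples, and in other decision-making measures. It gives no Domain factor, no comparison of effects between domains, no equivalence margin and no statement of which pattern of results would count as specific. The moderator and dosage regressions that follow are confined to ACT, and the mediation analysis concerns performance on the training modules. None of these compares ACT with CON across domains.

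On the control arm, Study design says that "those assigned to the attention-matched CON will complete games that use other brain attributes", and Control Training (CON) says its sessions "will utilize other Lumosity games that do not target working memory". The product as a whole "offers user-friendly cognitive training games targeting different brain areas". The eight CON games are neither named nor matched to the tests in Table 2, and there is no untrained arm.

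**The concern.** Specificity is a claim about a difference between effects: training helps working memory more than it helps other abilities. Separate models yield a set of separate p-values. The natural reading is that a significant working memory result beside non-significant results elsewhere shows specificity, but a difference in significance is not evidence of a difference in effect. With modest power, equal true effects will often fall on opposite sides of 0.05.

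The active control adds a second difficulty. If CON games improve a comparator domain about as much as ACT does, the ACT-CON difference there is close to zero although ACT did help. A broad benefit would again look confined to working memory. At stake is how the intervention's action is described, not whether it affects working memory.

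**Working it through.** **1. What is tested and what is asked.** Let D(WM) be the ACT-CON difference in mean change in working memory, and D(j) the same for domain j. The plan tests D(WM) = 0 and, separately, D(j) = 0. The specificity question concerns D(WM) - D(j), which is not tested.

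**2. Inputs.** From the documents: two arms, simple random assignment, and seven Table 2 domains besides working memory (attention, executive function, learning, memory, processing speed, motor, verbal fluency). The plan gives no sample size, effect size, alpha or power, so there is no figure to reproduce. Assumed: 30 per arm, two-sided alpha 0.05, a true effect of 0.5 SD of change in every domain (a fully general benefit), and correlation 0.4 between changes.

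**3. Power of each separate model.** Noncentrality = d × √(n/2) = 0.5 × √15 = 1.94; the critical t on 58 df is 2.00; power = 0.478.

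**4. How often a general benefit looks specific.** For one comparator with independent changes, p(1 - p) = 0.478 × 0.522 = 0.25. At correlation 0.4, by simulation:

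| Rule for reading the effect as specific (working memory significant in each case) | Share of trials |
|---|---|
| One given comparator non-significant | about 18% (18.4% to 18.8% in repeat simulations) |
| Most of the seven non-significant | about 16% |
| All seven non-significant | about 1.4% |

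Among trials with a significant working memory result, the one-comparator pattern arises in 0.188 / 0.479 = 39%. A direct test of D(WM) - D(j) rejects in 5.0% of trials, about half of them in working memory's favour.

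**5. Range.** Over 20 to 40 per arm and 0.4 to 0.8 SD at correlation 0.4, the one-comparator rate runs from about 5% to 19%, and the all-seven rate is at most about 3%. Over a wider grid (20 to 60 per arm, 0.3 to 0.8 SD, correlation 0 to 0.6), the rates are 0.6% to 25% for one comparator and at most 4.7% for all seven.

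**6. If CON trains the comparators.** Suppose ACT gains 0.5 SD everywhere and CON also gains 0.5 SD in the comparator. Then D(WM) = 0.5 and D(j) = 0. The one-comparator pattern appears in about 45% of trials (0.478 × 0.95 = 0.454). If CON trained all seven equally, the all-seven rule would be met in about 36% (correlation 0.3). The direct contrast does not cure this: it rejects in about 41% against one comparator, and in 58% against the mean of seven at correlation 0.3. In ACT-CON terms this scenario is identical to true specificity, so no contrast between these two arms can separate them.

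**7. True null everywhere.** Working memory is significant in ACT's favour in 2.5% of trials; with one comparator non-significant, about 2%; with all seven, about 1.3%. There is no inflation.

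**The case against.** The strongest reply is that the plan states no rule for declaring specificity and nowhere says that non-significance means no effect. The rule is supplied by the reader, and the error rate moves with it. This stands. A reader might infer that the planned method gives false specificity claims well above 5%. The documents do not support that as a general statement, since a strict all-seven rule keeps the chance error below 5% throughout the grid.

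Two other stronger readings are tempting. One is that a null effect could be passed off as specific; step 7 shows only the ordinary false-positive rate. The other is that CON does train several tested domains. The documents make this possible, but no CON game is named, and the 45% figure needs CON to match ACT's gain and that gain to carry over to the neuropsychological test.

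It is also fair to say that the Time term would show improvement in both arms, although mixed with practice effects; that specificity is not among the listed aims or hypotheses; and that the attention-matched control already addresses non-specific engagement. These points limit the importance. They do not supply the missing comparison between domains.

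**Conclusion.** The point holds as a cheap improvement, not as an error in the main analysis. The plan announces an examination of specificity, and the models it names cannot show that the working memory effect exceeds the others. Under the assumed 30 per arm, 0.5 SD general effect, correlation 0.4 and two-sided 5% tests, the chance of a misleading pattern is about 18% judged against one comparator and about 1.4% if all seven must be non-significant. The plan does not say which reading applies. Separately, a null ACT-CON difference in a domain that CON games may train cannot be taken as no ACT effect there; the size of that problem is unknown until the games are matched to the tests. Every percentage rests on assumed inputs. The primary ACT-CON comparison on working memory is unaffected.

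**What to change.** - Add one pre-specified contrast: the ACT-CON difference in (working memory T-score change minus mean change in the comparator cognitive domains), with a 95% CI. Base any statement about specificity on it alone.
- Use comparator domains scored as T-scores, or standardise them to a common metric. The plan specifies a T-score only for working memory.
- Before unblinding, map the eight CON games to the test domains, and keep as comparators only domains that neither arm's games target. If none remain, report that specificity cannot be separated from CON training.
- Keep the per-domain models and the decision-making measures as descriptive results, with within-arm changes and CIs.

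The cost is SAP wording, the game mapping and some rescaling, all on data already being collected. There will be fewer comparators, and the specificity statement may be less favourable. Power is also limited: with a 0.5 SD effect truly confined to working memory, 30 per arm and correlation 0.3, the contrast is significant in 58% of trials against the mean of seven domains but in only 37% against a single domain. The CI should therefore carry the interpretation.
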